8.5.3.2. Food-Effect

For Part 2 a statistical analysis will be conducted to investigate the food-effect by comparing treatments EIDD-2801 (fed) to EIDD-2801 (fasted) for PK parameters of EIDD-2801 and EIDD-1931 ($AUC_{0-\text{inf}}$, AUC_{last} , and C_{max}). If an additional cohort is enrolled with a different dose level then that cohort will be analyzed in a separate model.

The natural log (ln)-transformed PK parameters will be analyzed using a mixed model.⁶ The model will include planned treatment sequence, period, and actual treatment as fixed effects, and subject within planned treatment sequence as a random effect.

For each PK parameter separately, the least squares mean (LSM) for each treatment, difference in LSMs between the fed and fasted treatments, and corresponding 90% CIs will

be calculated; these values will then be back-transformed to give the GLSM, ratio of GLSMs, and corresponding 90% CI.

Additionally, the pooled estimate (across all treatments) of the within-subject coefficient of variation (CV) will be calculated, and residual plots will be produced to assess the adequacy of the model(s) fitted.

A statistical analysis using the Wilcoxon signed-rank test⁷ will be conducted to investigate the food-effect on the treatment by comparing the fed treatment to the fasted treatment for t_{max} . The median for each treatment, Hodges-Lehmann estimate of the median difference between the fed and fasted treatments, and corresponding 90% CIs will be calculated.

Examples of the SAS code that will be used are as follows:

Mixed Model Analysis

```
proc mixed data = <data in>;  
  by parcat1n parcat1 pckday paramn param;  
  class trtan aperiod trtseqp usubjid;  
  model lpk = trtan aperiod trtseqp / cl residual ddfm = kr2;  
  lsmeans trtan / cl pdiff = control('1') alpha = 0.1;  
  random intercept / subject = usubjid(trtseqp);  
  ods output lsmeans = <data out>;  
  ods output diffs = <data out>;  
  ods output covparms = <data out>;  
run;
```

Wilcoxon Signed-rank Test

```
proc univariate data = <data in> cipctldf(alpha = 0.1);  
  by parcat1n parcat1 pckday paramn param;  
  var ref test dif;  
  ods output quantiles = <data out>;  
  ods output testsforlocation = <data out>;  
run;
```

(Note: Derive Hodges-Lehmann estimates)

8.6. Safety and Tolerability Assessments

8.6.1. Adverse Events

All AEs will be coded using the Medical Dictionary for Regulatory Activities (MedDRA) Version 23.0 (or higher if upversioned during the study). All AEs will be assigned severity grade using the Division of Microbiology and Infectious Diseases (DMID) toxicity scale (March 2014).

A treatment-emergent adverse event (TEAE) will be defined as an AE that starts during or after dosing (Part 1)/the first dose (Part 2 and Part 3), or starts prior to dosing (Part 1)/the first dose (Part 2 and Part 3) and increases in severity after dosing (Part 1)/the first dose (Part 2 and Part 3).

A treatment-related TEAE will be defined as a TEAE with a relationship of possibly, probably, or definitely related to the study treatment, as determined by the investigator.

The assignment of TEAEs to treatments for Part 2 will be as follows:

- A TEAE occurring during or after Day 1 dosing and prior to Day 15 dosing will be assigned to the treatment given on Day 1 (period 1)
- A TEAE occurring during or after Day 15 dosing will be assigned to the treatment given on Day 15 (period 2)
- All AEs will be listed. In addition to the data recorded in the database, the listings will include derived onset time and duration. Onset time will be calculated from the time of dosing (Part 1)/dosing in each period (Part 2)/the last dose (Part 3) for TEAEs only.

The frequency of subjects with TEAEs and the number of TEAEs will be summarized for the following categories:

- TEAEs (overall, serious, leading to discontinuation, life-threatening, and leading to death) by treatment
- TEAEs by severity and treatment
- Treatment-related TEAEs (overall, serious, leading to discontinuation, life-threatening, and leading to death) by treatment
- Treatment-related TEAEs by severity and treatment

The frequency of subjects will be summarized separately for TEAEs and treatment-related TEAEs by the following:

- System organ class, preferred term, and treatment
- Preferred term and treatment
- System organ class, preferred term, day of onset, and treatment (Part 3)

For the AE data the following rules will apply:

- For the derivation of TEAE status: If the start date/time of an AE is incomplete or missing, an AE will be assumed to be a TEAE, unless the incomplete start date/time or the end date/time indicates an AE started prior to dosing (Part 1)/the first dose (Part 2 and Part 3).
- For the derivation of treatment-related TEAE status: If the study treatment relationship for a TEAE is missing, a TEAE will be assumed to be a treatment-related TEAE.
- For the derivation of onset time: If the start date/time of an AE is missing, onset time will not be calculated. If the start date/time of an AE is incomplete, where possible, the minimum possible onset time will be calculated and presented in ‘≥DD:HH:MM’ format (eg, if the date/time of dosing (Part 1) is 01MAY2019/08:00 and recorded start date/time of an AE is 03MAY2019, then the minimum possible onset time will be calculated by assuming the AE started at the first hour and minute of 03MAY2019 [03MAY2019/00:00], thus will be presented as onset time ≥01:16:00 in the listing).

- For the derivation of duration: If the end date/time of an AE is missing, duration will not be calculated. If the start or end date/time of an AE is incomplete, where possible, the maximum possible duration will be calculated and presented in ‘≤DD:HH:MM’ format (eg, if the start of an AE date/time is 01MAY2019/08:00 and its recorded end date/time is 03MAY2019, then the maximum possible duration will be calculated by assuming the AE ended at the last hour and minute of 03MAY2019 [03MAY2019/23:59], thus will be presented as duration ≤02:15:59 in the listing).
- For the calculation of summary statistics: If the severity of a TEAE is missing, a TEAE will be counted under the maximum severity possible.
- For the calculation of summary statistics: If a subject experienced multiple TEAEs with the same preferred term for the same treatment, this will be counted as 1 TEAE for that treatment under the maximum severity recorded.
- If adverse events that change severity have a missing relationship, the relationship will be assigned to the same relationship as the original adverse event.

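### As written, the planned number of TEAEs counts subject-by-preferred-term pairs, not events, and so understates recurrent events

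*SAP*

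**What the plan says.** SAP section 8.6.1 promises two quantities for its overview and severity tables: "The frequency of subjects with TEAEs and the number of TEAEs will be summarized for the following categories". The categories are TEAEs overall (with serious, discontinuation, life-threatening and fatal subsets) and by severity, each repeated for treatment-related events.

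The tables by system organ class and preferred term, including a Part 3 table that also splits by day of onset, are different. They hold subject counts only: "The frequency of subjects will be summarized separately for TEAEs and treatment-related TEAEs by the following".

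The counting rule comes later in the section and opens "For the calculation of summary statistics: If a subject experienced multiple TEAEs". It provides that when a subject has "multiple TEAEs with the same preferred term for the same treatment, this will be counted as 1 TEAE for that treatment", and that this single TEAE is placed "under the maximum severity recorded". No exception is made for the event count.

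The same section also provides that "All AEs will be listed", with derived onset time and duration.

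**The concern.** Counting a subject once per term at the worst grade is the usual convention for subject frequencies. Here the rule says what counts as one TEAE, and the section also plans to report a number of TEAEs. Applied to that number, the rule gives a quantity that does not match its label: a reader of the study report will take it as the number of events.

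AEs are one of five components of the primary safety endpoints of Parts 1 and 3 (section 3.1, with laboratory tests, physical examinations, ECGs and vital signs). No inferential safety analysis is planned (section 8.6.6), so the descriptive tables are the AE analysis. Part 3 is where tolerability under repeated dosing is the question, and where one subject has the most opportunity to have the same event again on the same treatment.

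**Working it through.** The SAP states no figure on this point, so there is none to reproduce. The check has two parts: what the rule does to each planned table, and an illustration of size.

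**Inputs from the SAP**
- Planned Part 3 dosing (section 4.1.3): twice daily on Days 1 to 5 plus one dose on Day 6, so 2 × 5 + 1 = 11 doses. Section 6.3 puts all of them under one treatment label. The schedule may be changed during the study.
- Cohort size (section 5): 6 active and 2 placebo.
- Part 2 (section 8.6.1): TEAEs are assigned to the treatment of the period in which they occur, fed or fasted.

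**Effect on each table**
- *Number of subjects with TEAEs, and subject counts by class and term:* unchanged. A subject counts once with or without the rule.
- *Number of TEAEs:* becomes the number of distinct subject-by-term pairs per treatment. A term that follows both doses in Part 2 counts twice, because the two doses are different treatments. A term that follows all 11 doses in Part 3 counts once. The same label therefore means different things in different parts.
- *Number of TEAEs by severity:* a subject with 3 mild episodes and 1 moderate episode of one term has 4 episodes, but appears as 0 mild and 1 moderate.
- *Part 3 day-of-onset table:* not determined. It counts subjects, and the rule does not mention onset day. The SAP does not say whether a subject with a term on several days appears on each of them or only once.

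**Illustration 1: fixed recurrence.** Suppose all 6 active subjects of a cohort have k episodes of one term. Episodes = 6k; counted = 6; share counted = 1/k.

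| k | Episodes | Counted | Share counted |
|---|---|---|---|
| 1 | 6 | 6 | 100% |
| 2 | 12 | 6 | 50% |
| 3 | 18 | 6 | 33% |
| 6 | 36 | 6 | 17% |

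**Illustration 2: random recurrence.** Assume the episodes of one term per subject are Poisson with mean m. Expected episodes per subject = m; expected count under the rule = 1 − exp(−m); undercount = 1 − (1 − exp(−m))/m.

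| m | 6 subjects: episodes | 6 subjects: counted | Undercount |
|---|---|---|---|
| 0.1 | 0.60 | 0.57 | 4.8% |
| 0.3 | 1.80 | 1.56 | 13.6% |
| 0.5 | 3.00 | 2.36 | 21.3% |
| 1 | 6.00 | 3.79 | 36.8% |

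The values of k and m are assumptions. Both tables concern a single term. The planned totals run over all terms, so a frequently recurring term is diluted by terms that occur once.

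**The case against.** Five points can be made for the SAP.

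1. *The rule is open and gives a defined quantity.* This is true. The defect is a mismatch between that quantity and its label, in a section that deliberately plans an event count beside a subject count. It is not an undefined analysis.
2. *Collapsing has a purpose.* The section separately covers the case "If adverse events that change severity have a missing relationship", and contrasts such records with the original event. That suggests a change in severity may be entered as a new record, in which case an uncollapsed count would count one episode twice. This stands, and any fix must deal with it. It justifies linking records of one episode, not merging separate episodes.
3. *Recurrence is not hidden.* A reader might infer that the rule removes recurrence from the report. It does not: every AE is listed with onset and duration, and with 6 active subjects per cohort the recurrences can be read from the listings. The loss is confined to the summary counts.
4. *The day-of-onset table may be sound.* A reader might infer that it can show a recurring event on one day only. The SAP does not say so, and it gives no stated purpose for the table. The most that can be said is that its handling of recurrences is left open. The TFL shells, which section 1 names as the detailed description of the tables and which are not at hand, may settle this or footnote the count.
5. *Consequences are limited.* A reader might infer that the undercount flattens a dose-response or distorts escalation. No dose-response analysis of event counts is planned, and section 9 rests escalation on review of blinded safety and tolerability data. Nothing in the SAP ties it to these counts.

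Points 2 to 5 narrow the concern. None of them makes the event count a count of events.

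**Conclusion.** The point holds for the planned number of TEAEs, overall and by severity, for all and for treatment-related events. As written, it is a number of subject-by-preferred-term pairs per treatment. The direction is certain: any recurrence within a subject on one treatment lowers the count, and lower-grade episodes leave the severity breakdown.

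The size depends on recurrence rates that the SAP does not give. It is nil if no term recurs, and about 5% to 37% per term over assumed Poisson means of 0.1 to 1 per subject. Totals over all terms would show less than the most recurrent term does. Part 3 has the most room for undercounting, with 11 planned doses under one label.

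Subject frequencies are right as planned, and the listings keep every event. The day-of-onset table is a separate, smaller matter of missing specification. This should be corrected because two statements in one section do not fit together and the repair is cheap. It does not undermine the safety evaluation.

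**What to change.** In section 8.6.1:
- Limit the one-per-preferred-term, maximum-severity rule to subject frequencies.
- For the number of TEAEs, count each distinct episode. Link records that only document a change in severity of the same episode, and count them once at the highest severity.
- For the Part 3 day-of-onset table, state that a subject is counted once per preferred term per onset day.

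If the sponsor prefers to keep the present count, relabelling it as subject-by-preferred-term occurrences would remove the mislabelling, but would leave the report without an event count.

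The cost is SAP and table wording, a small programming change, and a rule for linking severity-change records. No new data are needed. Reported event counts will be higher wherever terms recur.

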5. SAMPLE SIZE JUSTIFICATION

No formal sample size calculation was conducted. The sample size of 8 per cohort (6 active: 2 Placebo) for the SAD and MAD cohorts is considered adequate for a Phase 1 FIH

study. The sample size of 10 subjects (all administered EIDD-2801) is in accordance with Food and Drug Administration (FDA) guidelines for sample size in food-effect studies.

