8.1.1. Calculation of the Summary Statistics

For continuous data the following rules will be applied:

- Missing values will not be imputed, unless specifically stated otherwise.
- Unrounded data will be used in the calculation of summary statistics.

- If the number of subjects with valid observations (n) < 3 , summary statistics will not be calculated, with the exception of n , minimum, and maximum.
- As Early Termination data is not associated with any scheduled timepoint, it will be excluded from all calculations of summary statistics.

For categorical data the following rules will be applied:

- If the categories of a parameter are ordered (eg, AE severity), all categories between the possible minimum and maximum categories will be included, even if $n = 0$ for a given category. If the categories are not ordered (eg, race), only those categories for which there is at least 1 subject represented will be included.
- Missing values will not be imputed, with the exception of AEs where the ‘worst-case’ approach will be taken (see [Section 8.6.1](#)), or unless specifically stated otherwise. A ‘missing’ category will be included for any parameter for which information is missing. This will ensure that the population size totals are consistent across different parameters.

All protocol deviations and data issues (eg, missing data or data outside of the protocol windows) that occur during the study, including those related to COVID-19, will be considered prior to database lock for their severity/impact on how the data will be displayed and analysed statistically.

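### Two SAP rules for a missing AE relationship conflict without stated precedence; for an AE that began before dosing and worsened afterwards, one would normally yield not related, against the worst-case approach

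*SAP*

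**What the plan says.** Four statements in the SAP bear on this.

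- **General policy (section 8.1.1, categorical data).** "Missing values will not be imputed, with the exception of AEs where the ‘worst-case’ approach will be taken". The sentence refers the reader to section 8.6.1.
- **What counts as a TEAE (section 8.6.1).** Besides events that start once dosing has begun, the definition takes in an event that meets a second condition: "or starts prior to dosing (Part 1)/the first dose (Part 2 and Part 3) and increases in severity after dosing". A complaint present before dosing that worsens afterwards is therefore a TEAE.
- **Missing relationship, general rule (section 8.6.1, rules for AE data).** "If the study treatment relationship for a TEAE is missing, a TEAE will be assumed to be a treatment-related TEAE". No exception is stated.
- **Missing relationship, severity changes (section 8.6.1, last rule in the same list).** "If adverse events that change severity have a missing relationship, the relationship will be assigned to the same relationship as the original adverse event". No condition is placed on when the original event began.

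On relatedness itself, section 8.6.1 says: "A treatment-related TEAE will be defined as a TEAE with a relationship of possibly, probably, or definitely related to the study treatment". The judgement is the investigator's.

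**The concern.** The last two rules overlap. A worsened event with no recorded relationship is a TEAE with a missing relationship, and it is also a severity change with a missing relationship. The SAP does not rank the rules, so two programmers could derive different flags from the same data.

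Copying is hardest to defend when the event began before dosing. The original record then describes something that happened before any drug was given, and it is not itself a TEAE. Only the worsening makes the event treatment-emergent. Copying lets a judgement about a pre-drug event settle whether an on-drug worsening is related to the drug, and the likely error is in the non-conservative direction.

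Adverse events are part of the primary endpoint in Parts 1 and 3 (section 3.1). Treatment-related TEAEs, overall and by severity, are planned summaries. Cohorts are small, so a single subject is visible in the table.

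**Working it through.** The SAP gives no figure to reproduce. The check is to apply both rules to every combination of relationship on the two records, and then to size one discordant subject.

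**Step 1: apply the rules.** *Worst case* means that a missing relationship on the worsened record is set to related. *Copy* means that a missing relationship on the worsened record takes the original's value, and worst case applies if that is missing too. *Possibly* stands for any of the related categories.

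| Worsened record | Original record | Worst case | Copy | Differ? |
|---|---|---|---|---|
| missing | missing | related | related | no |
| missing | not related | **related** | **not related** | **yes** |
| missing | possibly | related | related | no |
| not related | missing, not related or possibly | not related | not related | no (3 rows) |
| possibly | missing, not related or possibly | related | related | no (3 rows) |

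The rules disagree in 1 of 9 combinations: worsened record missing, original *not related*. The 9 combinations are not equally likely, so this count says nothing about frequency.

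**Step 2: see where that combination falls.** The SAP does not say what relationship is recorded for an event that starts before dosing. I assume it is normally *not related*, because no drug had been given. It could also be missing (the rules then agree on related) or, less plausibly, *possibly* (they agree again). Under the assumption, the discordant row is the usual one for a predose event that worsens and has no relationship recorded for the worsening.

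**Step 3: test whether either precedence resolves it.** If worst case always prevails, every missing relationship on a TEAE becomes related and the last rule has no effect on the treatment-related flag. If the last rule is to affect that flag, it must override worst case, and the discordant row then comes out as not related.

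**Step 4: size one subject.** Section 5 gives the cohort size: "The sample size of 8 per cohort (6 active: 2 Placebo) for the SAD and MAD cohorts". For one affected active subject with no other treatment-related TEAE:

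- under copy, the subject contributes 0/6 = 0%;
- under worst case, 1/6 = 16.7%;
- the difference is 16.7 percentage points.

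In the Part 2 cohort of 10 the same arithmetic gives 1/10 = 10.0 points. The number of such subjects is not in the SAP; taking 0 to 1 per cohort as an assumption, the range in Parts 1 and 3 is 0 to 16.7 points.

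**The case against.** The strongest reply is that the rules can be read in order. The general rule is introduced as a derivation of treatment-related status, while the last rule fills in the relationship value. One would fill the value from the original record first, then apply worst case to whatever is still missing. Carrying causality forward within one continuing event is a common convention. Section 8.1.1 also defers to section 8.6.1, so it is not fully independent evidence of a contradiction.

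Much of this stands. For events that start after dosing, the original judgement was made with drug on board and copying it is reasonable. The ordered reading is natural, but the SAP does not state it, and for predose events it produces the very result at issue.

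The consequences are also limited. No inferential safety analysis is planned (section 8.6.6), all AEs are listed, and the event stays in the all-TEAE and severity summaries. Escalation rests on sponsor and investigator review of blinded safety data (section 9), and the SAP does not tie it to this flag. The rule applies to placebo subjects as well, so no bias in the comparison with placebo is shown.

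A reader might infer three stronger claims that the SAP does not support:

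- **That every predose event worsening on drug is counted as unrelated.** The rule acts only when the relationship is missing; a recorded assessment of the worsening stands.
- **That such missing values are common, because a rule was written for them.** The SAP gives no frequency, and the blank may simply reflect how the case report form captures causality.
- **That Part 2 is biased because a period 2 worsening inherits a judgement made under the other dietary state.** Both periods give open-label EIDD-2801, relatedness is to study treatment, and an original that began in period 1 may itself be related.

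**Conclusion.** The concern holds in a narrow form, as a minor point. Two rules in the same list conflict, with no stated precedence, when a severity-change record has no relationship and the original is *not related*. For an event that began before the first dose, the copy rule would normally give not related, which departs from the SAP's own worst-case approach.

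The effect is confined to the treatment-related summaries. It is 16.7 percentage points of a six-subject active cohort per affected subject, and may be nil in practice. This rests on two assumptions: that predose records normally carry *not related*, and that the subject has no other treatment-related TEAE.

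**What to change.** In the last rule of the section 8.6.1 list, limit copying to severity changes whose original record started during or after dosing (Part 1) or the first dose (Parts 2 and 3), and say that within that scope it takes precedence over the general rule. Add that a TEAE which qualifies only through worsening of a predose event, and whose relationship is missing, is treated as treatment-related under the existing worst-case rule.

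The cost is a sentence or two in the SAP and one condition in the AE derivation. The downside is that a few worsenings of pre-existing complaints may be counted conservatively as related.
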